4.3.1.1 DATA VARIABLE TABLE

	Baseline Visit	Final Visit	Medical Record Review
Social History (age, sex, gender, housing/employment status, healthcare insurance coverage)	X	X	
Treatment history (methadone, buprenorphine, direct-acting antivirals, interferon, pre-exposure prophylaxis)	X	X	
Lifetime (ASI- drug of concern + injection drug use) 30 days (ASI)	X X	X	
HIV Risk Behaviors (RBS)	X	X	
Depression (PHQ-9)	X	X	
Anxiety (GAD-7)	X	X	
Value of Health (EQ-5D-5L)	X	X	
HCV Treatment experience/satisfaction		X	
Pharmacist care satisfaction		X	
Patient Navigator satisfaction		X	
Injection Network/Community Pharmacy Recommendation		X	
HCV Treatment Completion		X	X

Sustain Virologic Response (SVR12)			X
------------------------------------	--	--	---

4.3.2 DATA COLLECTION TOOLS

The primary method of collecting data will be completed electronically through REDCap. REDCap is a web-based HIPAA compliant platform that will be used to collect and export participant data. Each participant will have a unique Study ID (40XX) that will be used to distinguish their REDCap records. Identifiable participant information will be kept separately from participant data. In instances where paper assessments are used, those documents will be stored in a locked cabinet at Harborview Medical Center, separated from any identifiable patient information as well. Study ID assignments and participant names will be tracked through a password-protected Excel spreadsheet that will be stored on a secure drive accessible to only study staff. This Excel spreadsheet will also document information regarding study visits, including start date, the projected final visit date, and actual final visit date, as well as any study withdrawal details.

Further information about REDCap can be found in the [HepPSI REDCap Manual of Procedures](#).

4.4 PAYMENT TRACKING

After completing a research visit, research staff administering assessments will provide the participant their monetary reimbursement for the information they provided and their time. The reimbursements should be kept in an envelope when given to the participant. It is important that research staff track participant payments and document that the participant did in fact receive their payment. Research staff should carry paper copies of the Participant Payment Tracking Form and have the participant sign and date that they received their incentive. These forms should then be kept and locked in designated study file folders, away from any participant data. Additionally, at the bottom of the verification form is a HepPSI Payment Reference number. This number will be entered into the REDCap HepPSI Participant Tracking Database project in the “Participant Visit and Payment Log” form within each participant’s record.

Study staff should work with their office’s designated finance officer to determine the set-up and maintenance of field advances. Money and ATM card will be kept in a secure lock-box. Along with the money and ATM, the study staff should have a log of when the lock-box is accessed for proper tracking purposes. Research staff should also keep every ATM receipt as their office’s finance officer will need this to reconcile the budget and field advances later at the end of the budget year and end of project.

5 PARTICIPANT SAFETY

5.1 POTENTIAL RISKS

5.1.1 PSYCHOLOGICAL STRESS

There are no anticipated risks to participants' physical health during this study. However, there are other risks to be considered. Talking about sensitive topics may cause participants to feel uncomfortable or distressed. This will be minimized by training the research staff to look for signs of distress and provide reassurance. Participants will be reminded that they have the option to refuse answering assessment questions that cause undue distress. They will also be offered regular breaks during the assessment session.

5.1.2 LOSS OF CONFIDENTIALITY

Breach of security of data collected is a potential risk for study participants. To reduce this risk, all data analysis will be conducted on data identified by study ID only and will not include any direct identifiers. Only a unique ID will be used to identify individual data collection forms; no subject names will be recorded on data collection forms. A crosswalk file linking subject identifiers and unique ID will be stored in a separate location from the data. All data will be stored on secure server and access to the data will be restricted by means of unique login names and passwords. All study files with identifiable information will be kept in locked file cabinets in a private office space, and only research staff will have access.

5.2 PRIVACY AND CONFIDENTIALITY

Study staff will safeguard the confidentiality of personal data collected from study participants through the use of Study ID codes instead of names on all research materials. The link referencing code number to name will be kept in a password-protected file accessible by computers that are password protected, as will all files related to the study.

Any printed study materials will be marked with participant's code and kept in a locked file cabinet in a private office. No one other than study staff will have access to these materials. The list relating names to number codes will be destroyed at the end of the investigation.

Only trained and approved study staff (research assistants, coordinators or PI) will interview subjects. We will work to arrange assessments with participants at a time and location so they can have privacy.

Participants will be covered by the Certificate of Confidentiality. This will help protect participant privacy by allowing study team members to refuse to provide identifying information about participants even if asked to by a court of law. We will use the Certificate to resist any demands for identifying information.

This does not prevent participants from sharing information about themselves or a part of the research if they choose to do so.

5.2.1 REDCAP

Study staff will enter data captured in visits from all participants into REDCap. The system is password protected and restricted to study staff. Participant assessment data, screening data, and tracking/payment information are each stored in separate REDCap projects with different record IDs. Research staff will have paper copies of all assessments in case REDCap is not accessible to collect participant's information.

5.3 ADVERSE EVENTS AND SERIOUS ADVERSE EVENTS

5.3.1 DEFINITION OF ADVERSE EVENTS (AE)

Any unfavorable and unintended sign (including an abnormal laboratory finding), symptom or disease temporally associated with the use of a medical treatment or procedure, regardless of whether it is considered related to the medical treatment or procedure.

5.3.2 DEFINITION OF SERIOUS ADVERSE EVENTS (SAE)

An adverse event (AE) or suspected adverse reaction is considered "serious" if, in the view of either the investigator or sponsor, it results in any of the following outcomes: death, a life-threatening adverse event, inpatient hospitalization or prolongation of existing hospitalization, a persistent or significant incapacity or substantial disruption of the ability to conduct normal life functions, or a congenital anomaly/birth defect.

5.3.3 CLASSIFICATION OF AN ADVERSE EVENT

Adequate review, assessment, and monitoring of adverse events require that they be classified as to severity, expectedness, and potential relatedness to the study intervention. Study protocols will include a description of how adverse events will be classified in these terms and the appropriate course of action.

5.3.3.1 SEVERITY OF EVENT

Classifications include the following:

Mild: Awareness of signs or symptoms, but easily tolerated and are of minor irritant type causing no loss of time from normal activities. Symptoms do not require therapy or a medical evaluation; signs and symptoms are transient.

Moderate: Events introduce a low level of inconvenience or concern to the participant and may interfere with daily activities, but are usually improved by simple therapeutic measures; moderate experiences may cause some interference with functioning

Severe: Events interrupt the participant's normal daily activities and generally require systemic drug therapy or other treatment; they are usually incapacitating

Severity is not synonymous with seriousness. A severe rash is not likely to be an SAE. Likewise, a severe headache is not necessarily an SAE. However, mild chest pain may result in a day's hospitalization and thus is an SAE.

5.3.3.2 RELATIONSHIP TO STUDY INTERVENTION

The site investigator assesses the potential event relationship to the study intervention and/or participation. A comprehensive scale in common use to categorize an event is:

- **Definitely Related:** The adverse event is clearly related to the investigational agent/procedure – i.e. an event that follows a reasonable temporal sequence from administration of the study intervention, follows a known or expected response pattern to the suspected intervention, that is confirmed by improvement on stopping and reappearance of the event on repeated exposure and that could not be reasonably explained by the known characteristics of the subject's clinical state.
- **Possibly Related:** An adverse event that follows a reasonable temporal sequence from administration of the study intervention follows a known or expected response pattern to the suspected intervention, but that could readily have been produced by a number of other factors.
- **Not Related:** The adverse event is clearly not related to the investigational agent/procedure. – i.e. another cause of the event is most plausible; and/or a clinically plausible temporal sequence is inconsistent with the onset of the event and the study intervention and/or a causal relationship is considered biologically implausible.

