5.3.3.3 EXPECTEDNESS

AEs must be assessed as to whether they were expected to occur or unexpected, meaning not anticipated based on current knowledge found in the protocol, investigator brochure, product insert, or label. Categories are:

Unexpected - nature or severity of the event is not consistent with information about the condition under study or intervention in the protocol, consent form, product brochure, or investigator brochure.

Expected - event is known to be associated with the intervention or condition under study.

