8.3 ADVERSE EVENT FORM

HepPSI Phase II Adverse Event Report Form

Adverse event- Any unfavorable and unintended sign (including an abnormal laboratory finding), symptom or disease temporally associated with the use of a medical treatment or procedure, regardless of whether it is considered related to the medical treatment or procedure.

This form is to be completed by HepPSI Phase II Research staff upon notice of an adverse event and updated until event is resolved and all necessary parties are notified of the specific singular event.

Adverse Event Record ID:	_____
Date of Report:	Date report was written.
Name of staff completing report:	First and Last Name of Research Staff Person
Research Role of staff completing initial report	 Research Assistant  Research Coordinator  Co-Investigator  Primary Investigator
Date Research Staff became aware of event:	Date Staff became aware of event
How did Research Staff become aware of event:	 Electronic Medical Record  Informant: Who was the informant?  Other: How did you become privy to the event?
Date of Event:	When did the event occur?
Participant's Study ID:	_____
Description of Event:	Describe the event – what happened, how did it happen, how upset does the participant seem, etc.

1. Was the event serious?
 
 YES (please indicate reason)  NO
	 Death  Life-Threatening  Hospitalization  Persistent or significant disability/incapacity  Result in birth defect  Breach of Confidentiality  Other – Specify the other serious outcome		

2. Was the event related to study participation?
 
 YES (please indicate degree of relatedness)  NO
	 Possibly Related  Definitely Related	
Justification for degree of Relatedness Refer to DSMP to explain reasoning for selected degree of relatedness.
	

3. Was the event expected?
	 YES	 NO	

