Outcome of Event:	 Unresolved – yet to be reviewed by PI  Ongoing – PI reviewed, waiting for responses from necessary parties  Unknown (lost to f/u)  Resolved – No more further action required (Resolved Date: Click here to enter a date.)  Death (Date: Click here to enter a date.)	
Will the participant continue study involvement?	 YES	 NO

Additional Notes

Actions to be taken by HepPSI Phase II Research Staff for Events

Unanticipated Problems

If the event is 1) **serious**, resulting in at least one of the 5 listed outcomes and/or causes greater risk of harm than was previously known or recognized (i.e. "Other"); 2) either possibly or definitely **related to the participant's study involvement**; and 3) **unexpected**, then research staff must do the following for this unanticipated problem:

- Report to Site PI, [name] within 24 hours of becoming aware of the event ([contact])
- Report to NIDA PO within 24 hours by email and submit a written follow-up within 2 days of the event [*NIDA PO – [name] ([contact])*]
- Report to IRB
 - o UW – ([link to UW HSD IRB Reporting Guidelines](#))
 - If the event is a breach (risk or loss) of confidentiality – report event to IRB within 24 hours.
 - If the event did not result in breach of confidentiality but still an unanticipated event UW Research Team must report to IRB within 10 business days of the event

Events that are not unanticipated problems

If the event is not considered to be an unanticipated problem, then the event is considered an AE/SAE and will need to be reviewed by research team at the following weekly meeting. In addition, research staff then must do the following:

- Report to Site IRB
 - o UW – Report recommendations made by the ISM at yearly meetings as Reportable New Information.
- Report all AE/SAEs to NIDA PO at annual continuing review/progress reports (i.e. RPPR and 6-month review)
- Report all AE/SAEs to ISM during annual Data Safety Monitoring Meeting

ISM Reviews and Reports

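### Both related categories in Protocol 5.3.3.2 require a recognised response pattern, so a serious event of a genuinely new kind fits no category and misses the unanticipated-problem route

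*Protocol*

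**What the plan says.** **Relatedness (Protocol 5.3.3.2).** *Definitely Related* requires, among other things, that the event "follows a known or expected response pattern to the suspected intervention, that is confirmed by improvement on stopping". *Possibly Related* requires reasonable timing and, in addition, that the event "follows a known or expected response pattern to the suspected intervention, but that could readily have been produced by a number of other factors". The third category is reserved for this: "The adverse event is clearly not related to the investigational agent/procedure". It is explained by another cause being most plausible, by timing that does not fit, or by biological implausibility.

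**Expectedness (5.3.3.3).** An event is unexpected when its "nature or severity of the event is not consistent with information about the condition under study or intervention in the protocol" or in the other study and product documents listed there.

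**Trigger (8.3).** Question 1 asks about seriousness, Question 2 about relation to study participation (yes, with possibly or definitely; or no), and Question 3 about expectedness. If the answers are yes, yes and no, "then research staff must do the following for this unanticipated problem": notice to the site PI and to the NIDA program officer within 24 hours, written follow-up within 2 days, and a report to the IRB (within 10 business days, or 24 hours for a breach of confidentiality).

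**If the trigger does not fire (8.3).** The event goes to the weekly team meeting, to NIDA progress reports (including a 6-month review) and to the annual meeting with the Independent Safety Monitor. For the IRB, only the monitor's yearly recommendations are listed.

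**All SAEs (5.3.4).** Every SAE goes to the site PI within 24 hours. The PI is also to report all SAEs promptly to the safety monitoring bodies, unless the protocol specifies otherwise with IRB or DSMP approval.

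**The concern.** Relatedness and expectedness should be separate judgements, because the trigger combines them. Here the relatedness definitions already contain a test of whether the reaction is recognised. An event must look familiar to count as related and unfamiliar to count as unexpected. The two demands pull against each other for the events that the unanticipated-problem route exists to catch: serious, plausibly caused by the program, and of a kind not seen before.

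What is at stake is the 24-hour notice to the funder and the event-level report to the IRB. The SAE itself would still be recorded and would still reach the site PI.

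**Working it through.** No figure is at issue, so the check applies the definitions as a logical rule.

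**Inputs**
- K: the event follows a recognised response pattern (5.3.3.2).
- T: the timing is reasonable (5.3.3.2).
- Related = Definitely or Possibly. Both definitions include T and K, so Related implies K.
- Unexpected = nature or severity does not fit the listed documents (5.3.3.3).
- Trigger = Serious and Related and Unexpected (8.3).

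**Cases, each for a serious event with T true**

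| Case | K | Can be Related? | Unexpected? | Trigger |
|---|---|---|---|---|
| (a) Genuinely new kind | false | no | yes, by nature | cannot fire |
| (b) Known kind, unexpected severity | true | yes | yes, by severity | can fire |
| (c) Pattern known from a source outside the listed documents | true | yes | yes, by nature | can fire |
| (d) Known kind, expected | true | yes | no | does not fire, as intended |

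Case (c) arises because 5.3.3.2 does not say where the pattern must be known, whereas 5.3.3.3 measures expectedness against named documents.

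**Where case (a) lands.** It fails *Definitely* and *Possibly* because K is false. Suppose also that no other cause is more plausible and that a causal link is not biologically implausible. With reasonable timing, none of the grounds given for *Not Related* then applies. The event fits none of the three categories, yet Question 2 still has to be answered.

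**Whether another definition fills the gap.** The form says: "Refer to DSMP to explain reasoning for selected degree of relatedness". Section 5.4 carries the title of a data safety monitoring plan but covers oversight, the monitor's duties and meetings; it does not define relatedness. In the documents supplied, 5.3.3.2 is the only definition.

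**What remains for case (a).** Under 5.3.4 the site PI hears within 24 hours, and prompt reporting to the monitoring bodies is called for. The same section limits the 24-hour NIDA notice to SAEs that are unanticipated problems, and 8.3 gives the event-level IRB report only on that route. Those two steps drop out.

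**The case against.** The strongest reply is that the damage is small and judgement will repair it. Section 5.3.3.2 presents the scale as one in common use and has the investigator consider participation as well as the intervention. Question 2 asks about study participation, which is broader than a drug-type response. An investigator could tick *Possibly Related* for a new event, and a separate DSMP may define the term differently. The study is a 40-person, single-arm observational pilot, and 5.1.1 anticipates no risk to physical health. This stands as a limit on likely frequency and on certainty about actual coding. It does not remove the defect: ticking *Possibly Related* would mean departing from the only written definition, on a form that asks for the choice to be justified.

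A reader might also infer three stronger things that the documents do not support:

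- *That no event unexpected in nature can ever trigger the route.* Case (c) shows that it can.
- *That staff are forced to answer no to Question 2.* The definitions do not compel this, because the event need not meet *Not Related* either. They leave it unclassified.
- *That the monitor would first see the event up to 12 months later.* That follows only if the annual review in 5.4.1.2 and 8.3 overrides the prompt reporting of all SAEs in 5.3.4. The protocol does not say which governs. This inconsistency is separate from the relatedness wording and needs its own resolution.

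**Conclusion.** The concern holds in a limited form. As written, a serious event of a genuinely new kind, with reasonable timing and no better explanation, cannot be coded related and fits no relatedness category. The unanticipated-problem trigger therefore does not fire for it, and the 24-hour NIDA notice and the event-level IRB report are lost. One of the four cases examined is affected; the route is not empty overall, and the SAE still reaches the site PI.

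The conclusion assumes that staff apply 5.3.3.2 literally and that no separate DSMP supplies a different definition. Frequency cannot be estimated from the documents and may well be low. The change is still worth making, because a written rule misroutes the very events that it is meant to catch.

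**What to change.** 1. In 5.3.3.2, remove the response-pattern condition from *Possibly Related*. Suggested wording: *an event whose timing is reasonable and for which a causal role of the intervention or of study participation cannot be ruled out, although other factors could also explain it*.
2. Keep the pattern condition in *Definitely Related* only, and leave expectedness to 5.3.3.3 and Question 3.
3. State which category prevails when another cause is most plausible but a contribution cannot be ruled out, since the new wording and *Not Related* could both apply there.
4. Have the form in 8.3 cite 5.3.3.2 by number, or confirm that any separate DSMP uses the same definition.
5. Reconcile the prompt reporting of all SAEs in 5.3.4 with the annual monitor review in 5.4.1.2 and 8.3.

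The cost is one rewritten sentence plus short clarifications. Some more events will be coded possibly related; the documents do not allow the number to be estimated. No treatment rule, endpoint or analysis changes.

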5.3.3.3 EXPECTEDNESS

AEs must be assessed as to whether they were expected to occur or unexpected, meaning not anticipated based on current knowledge found in the protocol, investigator brochure, product insert, or label. Categories are:

Unexpected - nature or severity of the event is not consistent with information about the condition under study or intervention in the protocol, consent form, product brochure, or investigator brochure.

Expected - event is known to be associated with the intervention or condition under study.

5.3.4 ADVERSE EVENT (AND SAE) REPORTING

Adverse Events (AEs) and Serious Adverse Events (SAEs) have specific reporting procedures. AEs will be collected via REDCap. If REDCap is down, research staff should use the paper form **Adverse Event Reporting Form (See Appendix 8.3)**.

All AEs are collected on an Adverse Event Form that includes the date of the event, what occurred, actions taken by project staff, planned follow up (if any), whether the event appears to be related to the intervention, the seriousness of the event, and whether participant will continue in the study (see appendix). All AEs experienced by the participant during the time frame specified in the protocol (e.g., from the time of study drug administration through the end of the study intervention period) are to be reported.

Please note that the AE form contains a column to indicate whether the event is serious. Thus, SAEs are a subset of the reported AEs.

All SAEs, unless otherwise specified in the protocol and approved by the IRB or DSMP (as applicable), require expedited reporting by the Principal Investigator to the study's safety monitoring bodies. Serious adverse events will be reported to the site PI within 24 hours of research staff becoming aware of the event. SAEs that are unanticipated problems will be reported to the NIDA PO within 24 hours by email and a written follow up will be submitted within 2 days of the event.

Any IRB action response will be reported to NIDA PO within 3 days of the receipt of notice of the action.

